participate as part of a dyad. Based on Phase II observations, 90% of these Dyads (i.e., 25) will complete an intensive 8-week treatment cycle. Recognizing variability in the incidence of disease, we chose the more conservative sample size of 25 patients enrolling in the study as part of a dyad for each arm thus resulting in 25 Case Dyads and 25 Control Dyads or 100 patient-caregiver participants. Based on Phase II observations, 90% are estimated to complete the 8-week treatment cycle and study.

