## 4.4 Study Duration

### 4.4.1 Approximate Duration of Subject Participation

Case Dyads (patient and caregiver) will participate in the study for approximately a 10-week duration (study period week 1 (baseline) followed by 7 weeks of intervention and a post-study questionnaire completed by week 10), however Control Dyads may have a shorter study period as they will be identified and recruited after Case Dyads and our intent is to authentically represent an early, 8-week Oncology Care period. The end of the study is the completion of the post-period survey. We anticipate most patients' Oncology Care cycles occurring over an 8-week period, however the post-period survey may be completed 1-2 weeks post-Oncology Care. Providers will be asked to participate in a one-time interview at the post-period when all Case Dyads have completed the study.

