### 4.4.2 Approximate Duration of Study

We anticipate recruitment, consent, and enrollment of 115 Geisinger participants (65 patients and 50 caregivers) to occur over the course of seven (7) months. Patients are able to participate independent of having a caregiver; therefore, the number of Geisinger patients enrolled is reflective of this possibility. Our goal is to include 100 participants in our analysis (50 patients and 50 caregivers) organized as 25 Cases Dyads and 25 Control Dyads. Case and Control Dyads will be in the study for approximately an 8-10-week duration. Their study participation ends once they have completed the post-period survey. The post-period survey may be completed 1-2 weeks post-Oncology Care. We estimate that study participation for all Dyads will end within ten (10) months after recruitment begins.

Providers participation in the study will end once their interview has been completed. Provider interviews will take approximately two (2) months to schedule and complete. We anticipate enrolling up to 20 providers.

As we near the end of data collection, data analysis and reporting of the study findings will begin. We estimate that this work will take approximately six (6) months.

We estimate that the study duration is eighteen (18) months.

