Once appropriate MyGeisinger access has been received, the research assistant will activate the dyad in FCA intervention and provide an overview of FCA's features and functions and answer questions that arise (**Attachment U: RA talking points**). The dyad will be asked to use FCA throughout the course of Oncology Care and provided with technical assistance as needed. The research assistant will assist the dyad with troubleshooting and ask the dyad to confirm that they have at least a basic level of comfort in using FCA.

At the end of the 8-week study period, the dyad will be asked to complete a post-period survey (**Attachment C: Post-Treatment Survey Patient and Attachment D: Post-Treatment Survey Caregiver**) based on their stated format preference determined during consent – in clinic, electronically, or mailed survey. If the Post-Treatment Survey is completed in the clinic, the RA will help to facilitate completion of the survey on an iPad or laptop. If the post-period survey is completed by e-mail or mail, the patient and/or caregiver will receive a letter/email (**Attachment I: Initial Post-Treatment Patient Communication – Case and Attachment J: Version 1.10 – 5.24.2018**

**Initial Post-Treatment Caregiver Communication).** Patients and caregivers will receive unique Surveys. Follow-up will be made in one week to non-responders of the survey (**Attachment K: Reminder- Post Treatment Patient Communication – Case and Attachment L: Reminder – Post Treatment Caregiver Communication – Case**). Three total follow-up attempts will be made to non-responders approximately one week apart; attempts will be made if no data or incomplete data are received with the goal of obtaining completed surveys. Once the study team receives the completed survey, the patient and caregiver will each receive a \$25 gift card. The gift card will be mailed to each individual (**Attachment T: Compensation Letter**).

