#### 4.5.1 Study Flow Diagram

## 4.6 Primary Question

The primary endpoint will be difference in quality and performance metrics at the post-period associated with FCA **exposure**, evaluated between the Case Dyads and Control Dyads.

Aggregate means will be calculated for dyads and compared between groups. Sensitivity analyses may stratify these results by low-moderate-high FCA use. FCA exposure is designed to impact care coordination, patient satisfaction, patient and caregiver quality of life, perceived involvement in care, and symptom management, all quality indicators, over standard of care in control clinic sites where care coordination is less efficient, labor-intense, and often frustrating to patients and caregivers. Additionally, the Consumer Assessment of Healthcare Provider Survey, performance metrics, for Cancer Care and Health Information Technology scores for FCA users vs. controls is expected to be greater as controls would have standard of care with no additional enhancements and could utilize MyGeisinger portals.

Theoretical Domain	Parameter of interest operationalized	Perspective	Data sources or location
Quality of Care	
Patient Satisfaction with Service Quality Hospital operations and services; physicians and staff; endorsements for others
 
Family Satisfaction with Advanced Cancer Care Information giving, availability of care, physical care, psychosocial care
	Patient Caregiver	
Patient Survey Attachment A and C: Pre and Post Survey
 
Caregiver Survey Attachment B and D: Pre and Post Survey

Patient-Caregiver Outcomes	
Quality of Life Patient's functional scales, symptoms, financial impact and global health and quality of life ratings
 
Caregiver's own state, relationships, outlook, patient condition, finances, environment
 
Caregiver Burden Personal impact, other family members, medical issues, concerned about loved one
 
Clinical Outcomes Survival, remission, exacerbation, MD Anderson Symptom Inventory
	Patient Caregiver Caregiver Patient	
Patient Survey Attachment A and C: Pre and Post Survey
 
Caregiver Survey Attachment B and D: Pre and Post Survey
 
Caregiver Survey Attachment B and D: Pre and Post Survey
 
Epic EHR See section 4.8.1

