#### **I. Patient:**

- Study ID
- Patient Survey Responses
- Date of birth
- Date of death (where applicable)
- Gender

- Treatment Location (GMC, GWV, GCMC)
- Problem list diagnoses
- Outpatient Encounters
  - Date
  - Flag for interpreter used
    - # distinct specialties seen
  - Visit type
  - Provider ID
  - Provider type
  - Clinic/department/location/specialty
  - Diagnosis codes associated with visit (flag primary)
  - Disposition (completed/no-show/cancel)
- Inpatient Encounters
  - Admission date
  - Diagnosis codes associated with discharge (flag primary)
  - Location (e.g. ICU)
  - Discharge date
- ED encounter data
  - Date
  - Diagnoses associated with visit (flag primary)
  - Flag if resulted in an admission
  - MD Anderson Symptom Inventory
- FCA (Harmonized Care) Usage
  - Dates of log-on
  - All features accessed in the application including dates accessed and number of views
  - Interest and Information
    - Number of topics added
    - Number of events added
    - Number of photos added
  - Appointments
    - Number of calendars added
    - Number of appointments added
  - Care Partners
    - Number of care partners added
  - Medication Management
    - Number of medications scheduled
    - Number of questions added
  - Notes
    - Number of private notes
    - Number of shared notes
  - Profile

- Number of profile pictures added

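### EHR outcomes have no follow-up window common to both arms and no end point for patients who die, and 25 enrolled dyads per arm at 90% completion give about 90 analysed participants, not 100

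*Combined protocol and SAP*

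**What the plan says.** **End of participation.** Section 4.4.1 uses a single event: "The end of the study is the completion of the post-period survey." Section 4.4.2 says the same of Case and Control Dyads: "Their study participation ends once they have completed the post-period survey." Neither section covers death, withdrawal or a patient too ill to answer. Section 4.4.1 gives Case Dyads about 10 weeks and lets Control Dyads have less, because they are found after the Cases. Section 4.4.2 gives 8-10 weeks for both.

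**Outcomes.** The table in 4.6 lists the clinical outcomes "Survival, remission, exacerbation, MD Anderson Symptom Inventory" with the source "Epic EHR See section 4.8.1". It also lists hospital admissions, ED visits and missed appointments from Epic and Aria. Date of death is among the patient data elements in 4.8.1. The survey comparison in 4.6 and 4.8.1 uses dyad means from the post-period survey.

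**Reminders.** Section 4.5 says "Three total follow-up attempts will be made to non-responders approximately one week apart", and "attempts will be made if no data or incomplete data are received with the goal of obtaining completed surveys". The Control text matches. No step asks staff to check vital status first.

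**Numbers.** Sections 3.2 and 3.3 recruit until 25 patients and 25 caregivers are enrolled per arm. Section 4.2.1 sets 25 dyads per arm at enrolment and then says that "90% are estimated to complete the 8-week treatment cycle and study". Sections 4.2.1 and 4.4.2 aim for 100 participants in the analysis. Section 4.3 replaces a dyad only when the caregiver does not enrol. Section 4.8.2 gives 50 Case Dyads and 50 Control Dyads.

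**The concern.** Only a living patient who is well enough can return a survey. If that return is the only stated end, the patients with the worst course have no defined end, and follow-up for everyone else depends on arm and on how quickly they reply. Counts of deaths, admissions and ED visits over unequal periods cannot be read as a difference between Cases and Controls.

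The survey comparison has a related gap. Controls have no baseline survey, and even their demographics come from the post-period survey (4.3). A Control patient who dies early therefore leaves no survey record, while a Case patient leaves a baseline. The plan does not say how such losses are reported, or whether a dyad mean is formed from the caregiver alone.

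The analysed sample is also stated as if every enrolled dyad completes, although the plan expects one in ten not to.

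**Working it through.** **1. The plan's own figure (4.2.1).**
- Eligible at GMC in six months: 153 x 0.5 = 76.5, stated as 77.
- Consenting: 77 x 0.37 = 28.49, stated as 28.
- Completing: 28 x 0.90 = 25.2, stated as 25.

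All three reproduce. In this chain, 25 is the number who complete out of 28 who enrol.

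**2. What the recruitment rule gives.** Sections 3.2 and 3.3 stop at 25 enrolled, and 4.2.1 applies 90% to those 25.
- Per arm: 25 x 0.90 = 22.5 dyads.
- Both arms: 2 x 22.5 = 45 dyads = 90 participants, against 100 stated.
- Cross-check from 4.4.2: 50 caregivers enrolled and 50 analysed requires 100% completion. The surplus of 65 - 50 = 15 patients is there for patients without a caregiver, not for attrition.

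**3. Effect on precision.** The standard error of a two-group difference in means, in SD units, is sqrt(2/n).
- n = 25: sqrt(2/25) = 0.283.
- n = 22.5: sqrt(2/22.5) = 0.298.
- Ratio: 0.298/0.283 = 1.05, so about 5% wider.

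**4. The EHR window.** Two cut-offs are natural on the text.
- *Date of survey return.* Patients who never return one have no end, and late responders are followed longer. With a constant event rate r per week and the extremes of the 8-10 weeks in 4.4.2, expected events are 10r against 8r, a ratio of 1.25 with no true difference. If the windows happen to be equal, the ratio is 1.00. The plan does not say how much shorter the Control period may be, so 1.00 to 1.25 is an assumed range.
- *Date of data extraction.* Controls are recruited after the Cases they match, so a calendar cut-off tends to give them less follow-up.

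Neither gives the arms a common window.

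**5. How often the missing death rule would matter.** The documents give no mortality over this period. Assume 2%, 5%, 10% or 15%, with m the mortality.

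| m | Expected deaths per 25 (25m) | Chance of at least one among 50, 1 - (1 - m)^50 |
|---|---|---|
| 2% | 0.5 | 64% |
| 5% | 1.25 | 92% |
| 10% | 2.5 | 99.5% |
| 15% | 3.75 | about 100% |

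The case is likely to arise at least once across the whole range.

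**6. Survivor selection in the survey means (illustration only).** Assume 3 of 25 dyads lost in one arm and 1 of 25 in the other, each of which would have scored 1 SD worse. The completer contrast then misses (3 - 1)/25 = 0.08 SD. That is under a third of the 0.28 SD standard error in step 3.

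**The case against.** A reader might infer that survival is 100% by construction. The documents do not support this. Anyone who returns a survey was alive that day, but the plan takes survival from the EHR, collects date of death, and nowhere limits EHR outcomes to those who returned a survey. Over the assumed mortality range in the working, EHR survival would be 85% to 98%. Survival is also absent from the constructs that 4.8.1 names for comparison: satisfaction, quality of life, burden and coordinated care.

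A reader might also infer that reminders continue to deceased patients and bereaved caregivers. The plan does not direct this. Attempts are capped at three, the letters and scripts are in attachments not reproduced here, and 5.3 sends problematic clinical issues to the investigators at once. What can be said is that the written trigger is absent or incomplete data and that no vital-status check is stated.

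Nor does a death remove the dyad altogether. The caregiver has a separate survey, 4.8.1 plans caregiver-only comparisons, and EHR data remain.

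On numbers, the best defence is that 25 means completers, as in the chain from 28. That does not fit 4.2.1, which goes on to call the 25 patients enrolling, or the rule in 3.2 and 3.3 to recruit until 25 are enrolled, or the 50 caregivers both enrolled and analysed in 4.4.2.

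Finally, the study is non-randomised, openly described as biased (4.1), and its tests are descriptive only. That limits the consequences, and the 0.08 SD illustration is small. A descriptive comparison still needs a stated window and an account of who is missing.

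**Conclusion.** The point holds in this form and is worth correcting before analysis, though it does not undermine the study.

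- **Follow-up.** There is no end point for a patient who dies or cannot respond, and no common EHR window for the arms. The 25% figure assumes 10 against 8 weeks and a constant event rate.
- **Missing surveys.** Death, decline, withdrawal and simple non-response are not told apart, so selection by arm would be invisible. The documents give no input from which to size the bias; 0.08 SD rests wholly on assumed losses and scores, and a patient who has died has no score to miss.
- **Contact.** The absence of a stated vital-status check is a gap in the text, not evidence that inappropriate contact would occur.
- **Numbers.** About 22-23 dyads per arm, or 45 dyads and 90 participants, rather than 100. This rests on the plan's 90%, which comes from Phase II, run in one oncology clinic with twelve dyads, and is carried over to the Control sites. The loss of precision is about 5%. The inconsistency with the stated goal matters more.

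**What to change.** 1. In 4.4.1 and 4.4.2, follow EHR outcomes for the patient in every enrolled dyad to death or to one fixed day, counted from a start point defined the same way in both arms, whether or not the survey is returned.
2. Record a reason for each missing post-period survey (death, too ill, withdrawn, no response) and tabulate it by arm beside the primary comparison.
3. In 4.5, check the EHR date of death before the survey request and before each reminder, and send no request to a deceased patient. Leave any approach to the bereaved caregiver to a procedure agreed with the IRB. A blanket stop would discard the one post-period survey such a dyad can still give.
4. In 4.2.1 and 4.4.2, give the expected analysed number as about 45 dyads (90 participants) at 90% completion of 25 enrolled per arm. Reconcile this with the chain of 28 consenting and 25 completing, and with the 50 + 50 dyads in 4.8.2. If 25 completing per arm is what is wanted, the recruitment target in 3.2 and 3.3 would have to be 25/0.90 = 27.8, that is 28.

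The cost is protocol wording, one chart look-up per contact and one coded field in REDCap. Date of death and encounters are already extracted. The stated analysed number becomes slightly less favourable.

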### 4.4.2 Approximate Duration of Study

We anticipate recruitment, consent, and enrollment of 115 Geisinger participants (65 patients and 50 caregivers) to occur over the course of seven (7) months. Patients are able to participate independent of having a caregiver; therefore, the number of Geisinger patients enrolled is reflective of this possibility. Our goal is to include 100 participants in our analysis (50 patients and 50 caregivers) organized as 25 Cases Dyads and 25 Control Dyads. Case and Control Dyads will be in the study for approximately an 8-10-week duration. Their study participation ends once they have completed the post-period survey. The post-period survey may be completed 1-2 weeks post-Oncology Care. We estimate that study participation for all Dyads will end within ten (10) months after recruitment begins.

Providers participation in the study will end once their interview has been completed. Provider interviews will take approximately two (2) months to schedule and complete. We anticipate enrolling up to 20 providers.

As we near the end of data collection, data analysis and reporting of the study findings will begin. We estimate that this work will take approximately six (6) months.

We estimate that the study duration is eighteen (18) months.

## 4.5 Procedures

### Case Dyads:

The research assistant will approach all eligible patients in the clinic (**Attachment U: RA talking points**) to inform them of the FCA study opportunity. Patients will learn about the need to identify a caregiver who can participate in using FCA with them to enroll in the study, however patients can participate in the study regardless of caregiver participation. Also, as part of agreeing to participate the patient will need to have or establish a MyGeisinger account and the caregiver will need to have or establish proxy access to the patients' medical record (some caregivers may already have this access). Interested dyads (patient and caregiver) that agree to participate will provide consent (**Attachment F: Informed Consent - Controls**) and this will be electronically stored in REDCap by the Research Assistant, who will also facilitate access or registration to MyGeisinger for the patient and caregiver. Participants who do not receive a copy of their consent form at the time of consent will be mailed a copy of their consent form for their records (**Attachment BB: Consent Form Letter**).

Prior to enrollment in the Family Caregiver Application, the dyad will be asked to complete a Pre-Treatment Survey (**Attachment A: Pre-Treatment Survey Patient and Attachment B: Pre-Treatment Survey Caregiver**). The terms "Study Questionnaires" and "Surveys" are used interchangeably throughout this protocol and represent the same items. Patients and caregivers will receive unique Surveys. Electronic versions of the consent and survey will be available via REDCap (paper versions available upon request). Patients and caregivers can complete the consent and survey in the clinic at the baseline time point using a secure study device (i.e., study iPad with a secure link populated through REDCap) or in hard copy. When a survey is completed and returned to the study team, the patient and caregiver will each receive a \$25 gift card. The gift card will be mailed to each participant (**Attachment T: Compensation Letter**).

Once appropriate MyGeisinger access has been received, the research assistant will activate the dyad in FCA intervention and provide an overview of FCA's features and functions and answer questions that arise (**Attachment U: RA talking points**). The dyad will be asked to use FCA throughout the course of Oncology Care and provided with technical assistance as needed. The research assistant will assist the dyad with troubleshooting and ask the dyad to confirm that they have at least a basic level of comfort in using FCA.

At the end of the 8-week study period, the dyad will be asked to complete a post-period survey (**Attachment C: Post-Treatment Survey Patient and Attachment D: Post-Treatment Survey Caregiver**) based on their stated format preference determined during consent – in clinic, electronically, or mailed survey. If the Post-Treatment Survey is completed in the clinic, the RA will help to facilitate completion of the survey on an iPad or laptop. If the post-period survey is completed by e-mail or mail, the patient and/or caregiver will receive a letter/email (**Attachment I: Initial Post-Treatment Patient Communication – Case and Attachment J: Version 1.10 – 5.24.2018**

**Initial Post-Treatment Caregiver Communication).** Patients and caregivers will receive unique Surveys. Follow-up will be made in one week to non-responders of the survey (**Attachment K: Reminder- Post Treatment Patient Communication – Case and Attachment L: Reminder – Post Treatment Caregiver Communication – Case**). Three total follow-up attempts will be made to non-responders approximately one week apart; attempts will be made if no data or incomplete data are received with the goal of obtaining completed surveys. Once the study team receives the completed survey, the patient and caregiver will each receive a \$25 gift card. The gift card will be mailed to each individual (**Attachment T: Compensation Letter**).

The caregiver identified by the patient may not be present for appointments (e.g., caregiver resides out of state). In such cases, enrollment in the study will need to be coordinated over the phone and by email. When this occurs and as possible, the study team will match Case Dyads to Control Dyads who have remote caregivers, but given the logistics of enrolling Case patients, then Case caregivers, matching and recruiting Control patients, and then recruiting Control caregivers in the brief study period, this may be difficult to operationalize and therefore be a source of bias as the Dyads' situations differ by distance. The study staff will ask the patient to speak with the identified caregiver about their interest in participation. Once the study team receives confirmation from the patient, the RA will ask the patient to provide the caregivers name and contact information. The study team will then reach out to the caregiver to explain the study in more detail and determine their interest in participation (**Attachment V: RA Scripts**). The RA will facilitate the applicable MyGeisinger and Proxy Access (**Attachment S: Remote Caregiver Letter**) and send an e-mail to the caregiver to consent and complete the baseline survey (**Attachment G: Initial Recruitment Email Caregiver – Case**). Follow-up will be made in one week if the caregiver has not consented or completed the baseline survey (**Attachment H: Reminder – Pre-Treatment Caregiver Communication – Case**). Three total follow-up attempts will be made to non-responders approximately one week apart; attempts will be made if no data or incomplete data are received with the goal of obtaining completed surveys. Once the study team receives the completed survey, the caregiver will receive a \$25 gift card. The gift card will be mailed to each individual (**Attachment T: Compensation Letter**).

Once consent is obtained, the baseline survey is complete and all applicable MyGeisinger and proxy access has been set up, the RA will call the caregiver to activate them in FCA intervention, offer and provide technical assistance, and confirm that the participating caregiver has at least a basic level of comfort with the FCA (**Attachment V: RA Scripts**)

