This study is characterized as an exploratory evaluation as the design limits the generalizability of findings and these findings will be biased in several ways. First, the treatment clinic and clinicians have been intimately involved in the development and implementation of the FCA. This factor likely influences clinician adoption of the FCA in care and could be limiting factor in other settings where FCA may be tested. Additionally, sites were conveniently chosen and site-level factors may bias study findings. The administration of the study sites is centralized to infer some consistency with operational procedures however this is a limiting factor in this exploratory evaluation. Quality and performance metrics are not routinely collected in these outpatient settings. In the absence of system-level data to describe variation in care, the study will depend on study questionnaires to evaluate quality and performance, which is a limiting factor as the perspective is contained to the study participants rather than the aggregate patient-population at each site. Secondly, a convenient sample of patients receiving care at the study clinics will be recruited into the study on a first-come, first serve basis and without random assignment to treatment or control groups. Additionally, Case Dyads must enroll in MyGeisinger patient portal to use FCA and although not required for the study, we will encourage Control Dyads to enroll in MyGeisinger patient portal to minimize bias related to health literacy using technology. Another potential bias is that some caregivers may reside out of state and this distance may impact the quality of their relationship with the patient; every effort will be made to match Case and Control Dyads with similar spatial situations but this may be prohibitive given the project timeline. These factors limit the assumption that any observations associated with FCA are related to the treatment use as variation in patient factors or the quality of care at clinics may account for observed associations. Potential participants (patients) are reasonably expected to receive an intense, brief oncology care with multiple appointments thus offering the opportunity to measure the impact of FCA use. Dyads will not be randomly assigned to treatment or control but offered standard of care per the clinic site. The study team will provide hands-on technical assistance to Case Dyads and associated clinicians to facilitate implementation and observe key learnings. Changes from baseline to post-study period will be evaluated within the Case Dyads, but given the severity of the condition and brief study period, the project team expects to observe greater differences in post-study period indicators between Case Dyads vs. Control Dyads.

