### **Control Dyads:**

[figure not shown]
The research assistant will approach all eligible patients in the clinic to inform them of patient-caregiver study (**Attachment U: RA Talking Points**). Interested patients will be asked to identify a caregiver to participate, however patients can participate in the study regardless of caregiver participation. The dyad will provide consent (**Attachment F: Informed Consent – Control**) (eConsent). At the completion of the control participant's 8-week study period, the dyad will complete the post-period survey (**Attachment C – Post Treatment Survey Patient and Attachment D: Post Treatment Survey Caregiver**) based on their stated format

preference determined during consent - in clinic, electronically or mailed (**Attachment O: Initial Post- Treatment Survey Patient Communication – Control** and **Attachment P: Initial Post Treatment Survey Caregiver Communication – Control**). Patients and/or caregivers that do not complete the survey in one week will receive a reminder to complete the survey (**Attachment Q: Reminder- Post Treatment Patient Communication – Control** and **Attachment R: Reminder – Post Treatment Caregiver Communication – Control**). Three total follow-up attempts will be made to non-responders approximately one week apart; attempts will be made if no data or incomplete data are received with the goal of obtaining completed surveys. Once the study team receives the completed survey, the patient and caregiver will each receive a \$25 gift card. The gift card will be mailed to each individual (**Attachment T: Compensation Letter**). Participants who do not receive a copy of their consent form at the time of consent will be mailed a copy of their consent form for their records (**Attachment BB: Consent Form Letter**).

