## II. Caregiver:

- Study ID
- Caregiver Survey Responses
- Age
- Gender
- FCA (Harmonized Care) Usage
  - Dates of log-on
  - All features accessed in the application including dates accessed and number of views
  - Interest and Information
    - Number of topics added
    - Number of events added
    - Number of photos added
  - Appointments
    - Number of calendars added
    - Number of appointments added
  - Care Partners
    - Number of care partners added
  - Medication Management
    - Number of medications scheduled
    - Number of questions added
  - Notes
    - Number of private notes
    - Number of shared notes
  - Profile
    - Number of profile pictures added

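### Caregiver distance is a self-declared bias met only by best-effort matching, and no planned analysis deals with it in the Case v. Control caregiver and dyad-mean comparisons

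*Combined protocol and SAP*

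**What the plan says.** Section 4.1 (Description) lists distance among the study's biases: "Another potential bias is that some caregivers may reside out of state and this distance may impact the quality of their relationship with the patient". It then promises that "every effort will be made to match Case and Control Dyads with similar spatial situations but this may be prohibitive given the project timeline". Section 4.5 (Procedures, Case Dyads) repeats the promise in weaker form: "as possible, the study team will match Case Dyads to Control Dyads who have remote caregivers". It gives the practical obstacle as the sequence of "enrolling Case patients, then Case caregivers, matching and recruiting Control patients, and then recruiting Control caregivers in the brief study period", and concedes that "this may be difficult to operationalize and therefore be a source of bias as the Dyads' situations differ by distance".

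The rule that carries out the matching is in section 4.3 (Recruitment). It pairs Controls to Cases 1:1 on four patient characteristics: sex, age band, histology and stage. No caregiver characteristic is used. Matching starts once the Case caregiver has consented. On the Control side, 4.5 (Control Dyads) says: "Interested patients will be asked to identify a caregiver to participate". That happens when the patient is approached, after the patient has been picked from the record-based list.

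The caregiver list under Data Sources in 4.8.1 has a study ID, "Caregiver Survey Responses", age, gender and app usage. Section 4.8.1 plans chi-square, t and non-parametric univariate tests for Case v. Control, at caregiver level and on the mean of the patient and caregiver scores in each dyad. The only stratification mentioned is by level of app use and by time available for exposure. ANCOVA appears only for the pre-post change within Cases.

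**The concern.** Caregiver quality of life, caregiver burden and family satisfaction are among the parameters of the primary question (4.6). All three could plausibly depend on whether the caregiver lives with or near the patient. The comparison is non-randomised and post-only, and Controls have no baseline survey, so a pre-existing caregiver difference cannot be removed later through baseline scores. Section 4.1 justifies the post-only design by expecting no baseline difference between the groups, yet the same section allows that distance may differ.

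An imbalance need not arise by chance alone. The arms are different sites, and the requirement that the caregiver be, or intend to be, the patient's portal proxy applies to Cases only (4.2.2). The documents do not show which arm would have more remote caregivers, so the direction of any bias is unknown. If the plan is followed as written, a reader of the results may be unable to tell whether the bias occurred.

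**Working it through.** **1. The plan's own recruitment figures (4.2.1).** Halving the 12-month counts gives 153/2 = 76.5 (stated 77), 137/2 = 68.5 (stated 69) and 21/2 = 10.5 (stated 11). At GMC, 77 x 0.37 = 28.5 consenting (stated 28), and 28 x 0.90 = 25.2 completing (stated 25). These reproduce.

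**2. Room for selective matching.** The Control pool is 69 + 11 = 80. If the GMC consent and completion rates carry over (an assumption), 80 x 0.37 = 29.6 consent and 29.6 x 0.90 = 26.6 complete, against 25 needed. There is almost no surplus from which to choose Controls by distance.

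**3. How often a remote Case finds a remote Control.** Simulation with 25 Cases, 30 consenting Controls, exact matching, equal-sized patient strata, and an assumed remote share of 10%, 20% or 30% that is the same in both groups:

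| Patient strata | Remote Cases with a remote Control |
|---|---|
| 1 (distance only) | 73% to 90% |
| 8 | 27% to 54% |
| 16 | 16% to 37% |
| 24 | 10% to 29% |

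The small pool and the four patient factors limit the match as much as the recruitment order does.

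**4. Size of the shift.** Bias = (difference in remote share) x (remote-local difference in SD).
- Assumed 20-point imbalance (5 of 25) and 0.5 to 1.0 SD: 0.20 x 0.5 = 0.10 SD; 0.20 x 1.0 = 0.20 SD.
- Wider assumed range, imbalance 0.1 to 0.3 and effect 0.2 to 0.8 SD: 0.1 x 0.2 = 0.02 SD to 0.3 x 0.8 = 0.24 SD.
- Standard error at 25 v 25: sqrt(2/25) = 0.283 SD. The 95% half-width is t(48) x 0.283 = 2.01 x 0.283 = 0.57 SD.
- So 0.10 to 0.20 SD is 35% to 71% of the standard error, or 18% to 35% of the half-width.
- Imbalance expected by chance has SD sqrt(2p(1-p)/25), which is 0.085 at p = 0.1 and 0.130 at p = 0.3. A 20-point gap is thus 0.20/0.130 = 1.5 to 0.20/0.085 = 2.4 such SDs.

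Section 4.8.2 gives 50 dyads per group where the other sections give 25. I used 25. The bias formula does not involve the sample size.

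**5. Which comparisons are exposed.**
- Case v. Control caregiver tests: exposed.
- Case v. Control dyad means: exposed, because the caregiver score is part of the mean. If the two scores are equally weighted on one scale and distance affects only the caregiver's score, the shift is halved, to 0.05 to 0.10 caregiver SD.
- Within-Case pre-post and within-Case patient v. caregiver: no Controls are involved, so imbalance between arms cannot confound them.

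**The case against.** The protocol discloses this limitation itself, including the reason that the recruitment order creates, and it declares the study exploratory with descriptive tests. Both points stand, and they limit the weight of the concern. They do not explain why nothing in the analysis uses the factor that was disclosed.

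A reader might go further in three ways that the documents do not support.
- **That matching on distance is practically impossible.** The text says only that it may be difficult or prohibitive. The Case caregiver's situation can be known before matching starts, and a Control patient names a caregiver at recruitment, so remote status can emerge before a pair is fixed. An approached Control could also be paired with a different Case. On distance alone, the simulation matches most remote Cases.
- **That distance is not recorded.** It is not listed by name, but survey responses are, and demographics are collected through surveys that are not in the documents. They may ask about residence. Remote caregivers in both arms also enrol by a separate phone and e-mail route.
- **That every caregiver comparison is biased.** Only those against Controls are exposed, and only if the remote share differs between arms.

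It is also fair to object that the effect sizes are assumed throughout, that a distance coefficient will be imprecise if few caregivers are remote, and that exposure remains confounded with site whatever is done here. All three stand.

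**Conclusion.** The concern holds in a limited form. The plan names a confounder, relies on a matching effort that it doubts and that its own matching rule omits, and plans no adjusted, stratified or restricted result. Any imbalance in remote caregivers passes unaltered into the Case v. Control caregiver comparison and, diluted, into the dyad-mean comparison.

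The size cannot be derived from the documents, which give neither a remote share nor a distance effect. The 0.10 to 0.20 SD shift is smaller than the sampling uncertainty at 25 v 25, but it is not trivial beside the standard error, and enrolling more dyads would not remove it. This is a low-cost improvement that the sponsor should make. It is not a flaw that invalidates an exploratory study.

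**What to change.** - **Matching:** keep matching on distance as best effort. There is no need to abandon it, but it should not be the only safeguard.
- **Data:** at consent, in both arms, have the research assistant record each caregiver's status as living with the patient, local or remote. Add the item to the caregiver list in 4.8.1 and report it by arm. If the surveys already ask it, name that item instead.
- **Analysis:** in 4.8.1, add a Case v. Control caregiver result and dyad-mean result adjusted for this status and for the caregiver age and gender already collected, shown beside the unadjusted result. If few caregivers are remote, give a result restricted to non-remote caregivers instead.

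**Cost:** one extra field, and about 2 + 1 + 1 = 4 degrees of freedom with about 50 caregivers (three-level status, age as a linear term, two-level gender). The distance coefficient will be imprecise if remote caregivers are few, and the restricted version loses those dyads. Neither version removes the confounding of exposure with site, and the report should say so.
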